2. Subjects on placebo in Part 1 are no longer allowed to enter Part 2 to receive open-label pexidartinib. After completion of the end of Part 1 assessments (Part 1 Completion visit/Early Termination visit), subjects who wish to continue onto the open label part of this study (Part 2) will be unblinded and those on placebo will be discontinued; subjects on pexidartinib in Part 1 may continue into Part 2 to continue to receive pexidartinib.
3. Investigators and subjects must be informed of the new safety information and decide whether to continue in the study. If, after consultation with the subject, it is deemed to be in their best interest to continue treatment, the subject must be re-consented.
4. The frequency of liver function testing is increased, and gamma-glutamyl transpeptidase (GGT) is added to the laboratory panel.

Updated hepatic safety risk information as of December 2017; please consult the IB for more information. Hepatotoxicity is an important adverse drug reaction. Elevations of liver transaminases and bilirubin have been observed in studies with pexidartinib, together with cases of drug-induced cholestasis. Cases of cholestasis have been observed in the first 8 weeks and have generally resolved with treatment discontinuation; however, some cases have been severe, with a protracted course requiring liver dialysis and, in 1 case, transplantation. Hepatotoxicity may be fatal. One fatal case with ongoing cholestatic liver injury at the time of death has been reported. Monitor patients closely as defined in the protocol. Protocol-defined dose reductions and discontinuations of pexidartinib, increased frequency of laboratory monitoring, and reporting of findings should be followed. In addition, rechallenge with pexidartinib should not be attempted without prior discussion with the Sponsor's Medical Monitor.

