MRIs will be performed at Week 13 (Cycle 4, Day 1 visit of Part 1 [P1-C4D1]) and Week 25. If disease progression is indicated clinically or by local radiologic assessment according to RECIST 1.1 at or after Week 13 but before Week 25, the Investigator may request a central review for evaluation of disease progression. Any disease progression before Week 25 must be verified by a central MRI reading. If a central reading confirms RECIST 1.1-defined disease progression, treatment assignment will be unblinded, and subjects receiving placebo will be eligible for early entry into Part 2 of the study. Effective 30 Sep 2016, subjects receiving placebo will be discontinued instead of being eligible to enter Part 2. Subjects receiving pexidartinib will be discontinued from the study unless the Investigator and the Sponsor's Medical Monitor judge that the subject would potentially benefit from continued treatment with pexidartinib. For those subjects who undergo surgical resection after Week 25, an MRI will be performed 4 months after surgery.

Part 2 will continue until all subjects have either reached at least the Week 49 visit, ie, an additional 24 weeks of study treatment beyond the placebo-controlled phase, or withdrawn from the trial (Figure 3.1). As in Part 1, dose reductions, interruptions, and re-escalations after previous reductions for toxicity are permitted according to pre-specified guidelines. Subjects who complete Part 2 will be eligible to continue pexidartinib treatment for study of longer efficacy and safety follow-up assessed per the schedule in Part 2 or to enter a separate protocol to continue receiving pexidartinib.

Figure 3.1: Study Schematic*

* Effective 30 Sep 2016, subjects on placebo are no longer allowed into Part 2 to receive open-label pexidartinib.

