15.3.15. Part 2–Cycle 10+, Day 1 (P2-C10+D1; Week 61+) ± 7 days

The procedures described below are performed at P2-C10D1 ± 7 days and every 12 weeks thereafter (eg, P2-C13, P2-C16).

To be performed within (±) 7 days of the visit:

- MRI of the affected joint (with local assessment of progression status);
- Third-party blinded range-of-motion assessment of the affected joint.

To be performed *before* any invasive procedures:

- Vital signs, including blood pressure, pulse rate, and oral temperature;
- PRO instruments, in the following order:
 - BPI Worst Pain NRS Item
 - Worst Stiffness NRS item
 - PROMIS Physical Function Scale
 - EQ-5D-5L

Other procedures to be performed:

- Dispense study treatment bottles.
- Review outpatient PRO instruments;
- AE assessment;
- Concomitant medications, including analgesics;
- Treatment compliance assessment;
- Physical examination;
- Clinical laboratory tests — serum chemistry, hematology, liver function, serum pregnancy testing (if applicable);

- Analgesic use assessment;

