AE = adverse event; ALT = alanine aminotransferase; AST = aspartate aminotransferase; BP = blood pressure; BPI = Brief Pain Inventory; C = cycle; D/d = Day; ECG = electrocardiogram; ECHO = echocardiography; End St./Ear. Term. = End-of-Study/Early Termination; EQ-5D-5L = EuroQol five-dimensional descriptive system; FSH = follicle-stimulating hormone; GGT = gamma-glutamyl transpeptidase; incl. = including; LD = last dose; LH = luteinizing hormone; MRI = magnetic resonance imaging; MUGA = multi-gated acquisition; NRS = numeric rating scale; P = Part; PDy = pharmacodynamic; PGx = pharmacogenomic; PK = pharmacokinetic; PRO = patient-reported outcome; PROMIS = Patient-reported Outcomes Measurement Information System; PVNS = pigmented villonodular synovitis; temp. = temperature; Tx = treatment; Week = week

- ^a The Part 1 Completion (Week 25) Visit will serve as the first visit of Part 2 and will be designated as P2-C1D1. All procedures listed for this visit are for reference only and will already have been conducted at the Part 1 Completion (Week 25) Visit except for the following, which should be performed at this visit: (i) administering the morning dose of pexidartinib; (ii) dispensing the dosing diary; (iii) 2-hour post-dose ECG; and (iv) dispensing the analgesic use diary.
- ^b Starting with P2-C10 (Week 61), subjects will return to the clinic every 12 weeks (ie, P2-C13, P2-C16, etc.) to undergo the procedures indicated.
- ^c If the subject withdraws before completing Part 2 or completes Part 2 but declines to continue treatment for study of longer efficacy and safety follow-up or in the separate continuation study, the post-treatment procedures should be completed 28 ± 7 days after the last dose of study treatment and before initiating any new PVNS therapy, including surgery. Subjects who complete Part 2 without experiencing progression or intolerability, or subjects who undergo surgical resection of their tumor after study treatment will be eligible to continue for longer efficacy and safety follow-up or to enter a separate protocol to continue receiving pexidartinib or for surgical data collection. Subjects who enter the separate protocol will not undergo Post-treatment and End-of-Study Visits.

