- ^d Effective 30 Sep 2016, subjects who wish to continue onto the open label part of this study (Part 2) will be unblinded after completion of the end of Part 1 assessments (Part 1 Completion visit/Early Termination visit) and those on placebo will be discontinued; subjects on pexidartinib in Part 1 may continue into Part 2 to continue to receive pexidartinib. If the patient is known to have been on pexidartinib treatment in Part 1, then visits and associated procedures are only required on Day 1 of each cycle in Part 2.
- ^e The End-of-Study/Early Termination MRI need not be performed if new PVNS therapy begins within 4 weeks of the Post-treatment Visit. Before or at the End-of-Study/Early Termination Visit, plans for any new PVNS therapy will be obtained. Details of any surgical treatment will be obtained per Footnote **u**.
- ^f A physical examination by study staff, MRI, blinded range-of-motion assessment of the joint location by a third-party examiner not otherwise affiliated with the trial, and administration of the PRO instruments are performed at all of the indicated visits including the P2-C4D1 visit, every 12 weeks thereafter (ie, P2-C7D1, P2-C10D1, etc.), and at the Post-treatment Visit. Vital sign assessment,

- clinical laboratory studies (chemistry, hematology), and PK/PDy blood sampling will be performed at all of the indicated visits, including the P2-C4D1 visit, every 12 weeks thereafter (ie, P2-C7D1, P2-C10D1, etc.), P2-C5D1, and P2-C6D1. [NOTE: On study visit days, the PRO instruments, including the EQ-5D-5L, should be administered before performing any invasive procedures.]
- ^g A standard 12-lead ECG is performed 2 hours after dosing at the P2-C1D1 visit and before and 2 hours after dosing at the P2-C1D15 visit. The 2-hour post-dose ECG measurements should begin within 10 minutes of the 2 hour post-dose time point. Thereafter, the ECG and blood draw for hormone testing is performed before dosing at the C13D1 visit, every 24 weeks thereafter (ie, C19D1, C25D1, etc.), and at the Post-treatment Visit.
 - ^h ECHO or MUGA scanning should only be repeated if more than 3 months have elapsed since the last procedure. Subjects who show a reduced ejection fraction relative to baseline at the last visit should be followed until a stable ejection fraction is measured by two consecutive tests.
 - ⁱ Hematology only.

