 - ^j Alkaline phosphatase, ALT, AST, total and direct bilirubin, and GGT should be assessed weekly during P2-C1 beginning on Day 1, weekly during P2-C2 beginning on Day 1, biweekly during P2-C3 beginning on Day 1, and on Day 1 of every cycle thereafter. More frequent monitoring is required in the case of increased liver function tests (see Section 5.3).
 - ^k Subjects receiving concomitant warfarin should have their anti-coagulation status carefully monitored for any necessary dose adjustments (see Section 5.3).
 - ^l Women who are not using hormonal contraception will be tested for levels of FSH, LH, progesterone, and estradiol. Hormone testing will not be required for women who have either had an oophorectomy or are post-menopausal. Men will be tested for levels of LH, FSH, and testosterone. Men whose testosterone level is below baseline at the last study visit should be followed until their level has stabilized or returned to baseline.
 - ^m Subjects should be reminded to complete the BPI Worst Pain NRS item and Worst Stiffness NRS item for at least 4 of 7 consecutive days prior to Day 1 of P2-C4, P2-C7, P2-C10, and before the Post-treatment Visit.
 - ⁿ The investigator may request a centrally read MRI to confirm progression as detailed in the Imaging Charter.
 - ^o For subjects who discontinue the study before completing Part 2 or complete Part 2 but decline to continue treatment for study of longer efficacy and safety follow-up or to enter the separate continuation study for reasons other than progression, the end-of-study or early termination MRI should be completed 12 weeks \pm 7 days after the last dose of study treatment or before starting any new PVNS therapy, including surgery, whichever occurs first. Subjects who withdraw from the study with progression do not undergo an End-of-Study/Early Termination MRI.
 - ^p A range-of-motion assessment in the affected joint or tumor location will be performed by a blinded independent third party assessor.
 - ^q Details on blood sampling are found in Section 6.4.16 (PK) and Section 6.4.15 (PDy).
 - ^r The morning dose of pexidartinib should be administered in the clinic at all of the indicated time points.
 - ^s Dose administration by the subject at home.
 - ^t AEs are monitored throughout the study via safety assessments, observation, and subject reporting (see Section 6.4.17).

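### Liver testing after Week 49 and post-treatment contraception are each set by sections that disagree, so a site following one section alone can fall short of the stricter rule

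*Combined protocol and SAP*

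**What the plan says.** **Liver tests.** In Table 15.3 (Section 15.13), footnote j is attached to the liver-function row. After weekly testing in Part 2 Cycles 1 and 2, it asks for tests "biweekly during P2-C3 beginning on Day 1, and on Day 1 of every cycle thereafter" and gives no end point. Footnote b says that from Cycle 10 (Week 61) "subjects will return to the clinic every 12 weeks (ie, P2-C13, P2-C16, etc.) to undergo the procedures indicated". Section 15.3.15, whose list includes liver function, sets its procedures at Cycle 10 "and every 12 weeks thereafter (eg, P2-C13, P2-C16"), and the same list includes "Dispense study treatment bottles". The table columns go from C7 (Week 49) directly to C10+ (Week 61+).

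Footnote f, which describes the 12-weekly laboratory work, says that "clinical laboratory studies (chemistry, hematology), and PK/PDy blood sampling will be performed at all of the indicated visits"; it does not name liver tests. Footnote d and the opening of Section 15.3 limit visits, for subjects known to have had pexidartinib in Part 1, to Day 1 of each cycle. Section 3.1 lets subjects who complete Part 2 stay on for "longer efficacy and safety follow-up assessed per the schedule in Part 2", so the same table governs extended treatment. The safety measures introduced on 30 September 2016 (cited in Section 6.4 as Section 1.6) include this one: "The frequency of liver function testing is increased".

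**Contraception.** Section 5.4.2 advises females to use a non-hormonal method, and males an effective one, until 1 month after the last dose. Section 1.5 requires birth control until 90 days after the last dose. Inclusion criterion 8 (synopsis and Section 4.1.1) runs to as much as 90 days after completion, does not define completion, and lists an IUD of either type as sufficient alone.

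**The concern.** The hold and stop rules for liver toxicity in Table 5.1 act only on a test result. The hepatic update before Section 2 warns that liver injury with this drug can be fatal. If a required test has no visit, an abnormality calling for a hold or permanent discontinuation can go unseen while the subject keeps taking drug dispensed for 12 weeks.

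For contraception, Section 1.5 reports that the drug was judged teratogenic in rabbits. Two different durations, and two different positions on hormonal methods, mean that what a subject is told depends on which section the site consults.

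Both are matters of subject safety and trial conduct. Neither touches the Week 25 comparison.

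**Working it through.** **Calendar.** Part 2 Cycle 1 Day 1 is Week 25 and cycles last 28 days, so Day 1 of cycle *c* falls at Week 25 + 4(*c* − 1).

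- C7: 25 + 4×6 = 49, as the table states.
- C10: 25 + 4×9 = 61, as the table states.
- C8 = 53, C9 = 57, C13 = 73, C16 = 85, C19 = 97.

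**Required against scheduled liver tests.** Section 7.6.3 counts resections up to 97 weeks of pexidartinib treatment, so treatment of that length is foreseen. From C8 to C19:

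- Footnote j: one test per cycle, 19 − 8 + 1 = 12.
- Footnote b and 15.3.15: C10, C13, C16 and C19, so 4.
- Without a visit: 12 − 4 = 8, and 8/12 = 67%.

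The ratio is two in three over any whole number of 12-week blocks, since each block holds three cycles and one visit. The nominal interval is 3 × 28 = 84 days against 28.

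**Delay in detection.** An abnormality that a C8 draw would show is seen at C10, 61 − 53 = 8 weeks or 56 days later. For C9 it is 61 − 57 = 4 weeks or 28 days. The ±7-day window on C10 moves the first figure to between 49 and 63 days.

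**Does other text supply the missing draws?**

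| Text | What it provides |
|---|---|
| Table 15.3 columns, footnote b, 15.3.15 | No visit at C8, C9, C11, C12 and so on |
| Dispensing row of Table 15.3 | C7, then C10+; no supply visit between them |
| Section 6.4.7 | Central tests at visits in the Schedule of Events; local tests to assess AEs or support dosing decisions |
| Footnote j, last sentence | More frequent testing once results are raised |
| Footnote d, opening of 15.3 | Day 1 of each cycle, for subjects on pexidartinib in Part 1 |

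Only the last row could supply a visit. Read as waiving the Day 8, 15 and 22 visits, it adds none. Read as requiring a Day 1 visit every cycle, it supports footnote j and contradicts footnote b and 15.3.15. It does not cover subjects who crossed over from placebo before 30 September 2016.

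**Contraception after the last dose.** Taking 1 month as 30 days, 90 − 30 = 60 days between Sections 5.4.2 and 1.5. On method, 5.4.2 is stricter for females; on duration it is weaker for both sexes. A female who uses a non-hormonal method that criterion 8 lists, for the longest stated period, satisfies all three sections.

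**The case against.** Footnote j is the specific rule on the liver row, and footnote b governs clinic returns without forbidding a blood draw between them. A site that reads both can comply, and the local-laboratory permission in Section 6.4.7 arguably covers tests that feed the dosing rules. This stands: the omission is a worst case for sites working from footnote b or 15.3.15 alone, and a reader who infers that the protocol has reduced liver testing to every 12 weeks goes beyond the text.

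Intent is also open. Footnote f's silence on liver tests suggests that footnote j was meant to be more frequent. But the table has no C8 or C9 column, so footnote j may have been drafted with the earlier cycles in mind. The documents do not settle this.

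Reported cholestasis arose in the first 8 weeks, so the affected period lies outside the window of those cases. It would be wrong to infer that monitoring is missing when those cases occurred.

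On contraception, 5.4.2 is advice and 1.5 is a requirement, so 5.4.2 does not cancel the 90 days. A reader might also count criterion 8's period from a late post-treatment visit and arrive at a much longer duration. With completion undefined, the documents support no particular figure of that kind. Section 5.4.2 is listed among the sections updated in version 10.0, so its shorter period may be deliberate. The consent wording, which also shapes what subjects are told, is not available here.

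These points limit the size and the certainty about intent. They do not make the sections agree.

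**Conclusion.** Both inconsistencies are in the current text and should be fixed. After Week 49, a site following footnote b or 15.3.15 alone omits two of every three liver tests that footnote j requires. The size assumes that no draw is made between visits and that footnote d is not read as creating monthly visits. How many subjects stay in this protocol past Week 49 is not given, since those completing Part 2 may move to a separate protocol, so the number of tests at risk cannot be stated.

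For contraception, a subject counselled from 5.4.2 alone stops about 60 days before the period in Section 1.5 ends, and the acceptability of a hormonal IUD alone is unresolved for females. The pregnancy-reporting window in Section 9.4 sets no contraception period and is not part of the conflict.

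**What to change.** **Liver tests.**

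- Keep footnote j, the stricter rule, unless the sponsor documents a reason for 12-weekly testing.
- Add to Table 15.3 and Section 15.3.15 a Day 1 liver draw for every cycle from C8, with a ±7-day window (as for Part 2 Day 1 visits from C3), and allow a local laboratory.
- State in footnote b that the 12-weekly interval applies to the other procedures.
- Reword footnote d and the opening of Section 15.3 so that they waive only the within-cycle visits and agree with this schedule.

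**Contraception.**

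- Set one duration, 90 days after the last dose, in Section 5.4.2 and in criterion 8 (synopsis and Section 4.1.1).
- Have the sponsor confirm this against the newer text of 5.4.2.
- Have the sponsor confirm whether a hormonal IUD alone remains acceptable. The stated rationale concerns ethinyl estradiol only.

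Send sites a clarification letter until the text is amended, and check that the consent form gives the same contraception rule.

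**Cost.** Two liver draws per subject per 12 weeks after Week 49 that have no visit now, though footnote j already calls for them. The rest is text. Sample size and analysis do not change.
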